9.1.2 Dose Reductions for Carfilzomib

	Carfilzomib
Baseline dose	36 mg/m ²
One level dose reduction	27 mg/m ²
Two level dose reduction	20 mg/m ²

	Carfilzomib
Baseline dose	56 mg/m ²

	Carfilzomib
One level dose reduction	45 mg/m ²
Two level dose reduction	36 mg/m ²
Three level dose reduction	27 mg/m ²
Four level dose reduction	20 mg/m ²

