9.2. Hematologic Toxicity

9.2.1 On day 1 of each new cycle, patients must meet the following criteria:

- $ANC \geq 1.0 \times 10^9 /L$
- Platelet count $\geq 50 \times 10^9 /L$

9.2.2 If these conditions are not met on Day 1 of a new cycle:

- The next cycle of treatment will not be initiated until the above conditions (section 9.3.1) are met. If ANC and platelet counts do not satisfy the requirements above after 2 weeks of withholding treatment, the subject will go off therapy. Transfusions and growth factors are permissible.
- For patients not meeting day 1 criteria (section 9.3.1) for two cycles (non-consecutive), the study drug dose(s) will be modified for the next cycle based on dose reduction tables of section 9.2.

9.2.3 If a patient develops thrombocytopenia or neutropenia during the cycle, then the following actions would take place (see Thrombocytopenia/Neutropenia table below).

Thrombocytopenia	Lenalidomide	Carfilzomib
Fall to $< 25 \times 10^9/L$	Hold both Lenalidomide and Carfilzomib, follow CBC at least weekly or more frequently if clinically indicated. Hold prophylactic anti-coagulation.	
Return to $\geq 25 \times 10^9/L$	Resume lenalidomide at next dose reduction	Resume carfilzomib at full dose.*
Subsequent fall to $< 25 \times 10^9/L$	Hold both Lenalidomide and Carfilzomib, follow CBC at least weekly or more frequently if clinically indicated. Hold prophylactic anti-coagulation.	
Return to $\geq 25 \times 10^9/L$	Resume lenalidomide at next dose level reduction	Resume carfilzomib at full dose.*

*Carfilzomib may be dose reduced at the clinical discretion of investigator.

Neutropenia (Absolute Neutrophil Count)	Lenalidomide	Carfilzomib
Falls to $< 0.5 \times 10^9/L$ or to $< 1.0 \times 10^9/L$ with fever	Hold Lenalidomide and Carfilzomib. Add filgrastim if Grade 3 with fever (single temperature of $38.3^\circ C$ or sustained temperature of $38^\circ C$ for > 1 hour) or Grade 4. Follow CBC at least weekly or more frequently if clinically indicated.	
Returns to $\geq 1.0 \times 10^9/L$	Resume Lenalidomide at next dose reduction.	Resume Carfilzomib at full dose.*
Subsequent drop to $< 0.5 \times 10^9/L$ or to $< 1.0 \times 10^9/L$ with fever	Hold Lenalidomide and Carfilzomib. Add filgrastim if Grade 3 with fever or Grade 4. Follow CBC at least weekly or more frequently if clinically indicated.	
Returns to $\geq 1.0 \times 10^9/L$	Resume Lenalidomide at next dose reduction.	Resume Carfilzomib at full dose.*

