*Carfilzomib may be dose reduced at the clinical discretion of investigator.

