9.3 Non-Hematologic Toxicities Requiring Dosing Modifications

- 9.3.1 Any \geq Grade 3 toxicity require appropriate study drug to be held until resolved to Grade 1 or baseline (unless specified below in tables 9.4.4) prior to resuming therapy or initiating next cycle. Investigator will determine which drug will be held based on side effect profile and clinical judgment. If therapy has been held for more than 2 weeks due to non-hematologic toxicity, the patient will be removed from protocol therapy.

- 9.3.2 Protocol therapy will be withheld for patients who require treatment of Grade 3 infection. If therapy has been held for more than 3 weeks due to treating a grade 3 infection, the patient will be removed from protocol therapy.
- 9.3.3 For patients experiencing \geq grade 3 toxicity (unless specified below in tables 9.4.4), subsequent doses will be reduced at next dose level (according to the tables in section 9.2) if the adverse event was deemed to be attributed to study drugs. If the adverse event was deemed to be unrelated to study drugs, the patient may continue the full dose.
- 9.3.4 Electrolyte or metabolic abnormalities that are reversible with electrolyte replacement within 48 hours or $<$ grade 3 infections that can be controlled by appropriate therapy are exempt from holding treatment or dose modifications.

Lenalidomide Toxicities	Specific Dosing Modifications
Blistering Rash (Any Grade)	Discontinue lenalidomide and remove patient from therapy
Venous thrombosis/embolism	Hold lenalidomide and start therapeutic anticoagulation. Restart lenalidomide at investigator's discretion at current dose level.
Renal Dysfunction CrCl based on Cockcroft-Gault formula: $\text{CrCl} = (140 - \text{Age}) \times \text{Mass (in kilograms)} \times [0.85 \text{ if Female}] \div 72 \times \text{Serum Creatinine (in mg/dL)}$	
 CrCl 31-60 mL/min – Dose reduce lenalidomide to 10 mg daily from Days 1-21 CrCl ≤ 30 mL/min (not requiring dialysis) – Dose reduce Lenalidomide to 15 mg every 48 hours CrCl ≤ 30 mL/min (requiring dialysis) – Decrease Lenalidomide to 5 mg daily and on dialysis days give lenalidomide dose after dialysis.
Infection (\geq Grade 3)	
Hold therapy, treat underlying infection.
 
Remove patient from therapy if treatment of grade 3 infection persists for more than 3 weeks.

Carfilzomib Toxicities	Specific Dosing Modifications

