13.0 CRITERIA FOR REMOVAL FROM STUDY

Off-therapy Criteria

If a patient is removed off-study during cycles 1-4, the patient is considered not evaluable, which will allow another patient to replace this slot.

- Patients with medically concerning grade 3 or 4 adverse events related to drug therapy may be taken off therapy at the discretion of the principal investigator.
- Patients who require more than 2 dose reductions of Carfilzomib.
- Hematologic toxicity has not completely resolved or resolved to < grade 1 or baseline after 2 weeks of withholding treatment
- Therapy has been held for more than 3 weeks due to treating a grade 3 infection
- Grade 4 non-blistering rash or blistering rash of any grade
- Grade 4 neuropathy
- Grade 4 hypersensitivity reaction
- Patient experiencing significant cardiac event as outlined in section 9.5
- Patient completes the protocol treatment
- Progression of disease
- Patient chooses to go off therapy
- The principal investigator may remove patient from protocol therapy if deemed necessary due to medical conditions, compliance, etc.
- Patient becomes pregnant.
- Patient has < PR after 4 cycles

Off-Study Criteria

- Patient requests to be withdrawn from study
- Death
- Physician's determination that withdrawal is in the patient's best interest.
Patient has completed 1- and 3-year evaluation from end of therapy

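### Section 13 and a Section 10 footnote differ from Section 9 on count recovery after a 2-week day 1 delay and on one dexamethasone dose; a minor ambiguity also surrounds the carfilzomib reduction cap in Cohort 2

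*Combined protocol and SAP*

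**What the plan says.** **Carfilzomib reductions.** The off-therapy list in Section 13.0 includes "Patients who require more than 2 dose reductions of Carfilzomib" and names no cohort. Section 9.1.2 has one table per starting dose. From 36 mg/m² (Cohort 1) the levels are 27 and 20. From 56 mg/m² (Cohort 2) they are 45, 36, 27 and 20, the last row labelled "Four level dose reduction". For non-hematologic toxicity, 9.3.3 states that "subsequent doses will be reduced at next dose level". For low counts, the note under the 9.2.3 tables says "Carfilzomib may be dose reduced at the clinical discretion of investigator", with no step size. The second bullet of 9.2.2, for patients who miss the day 1 criteria in two cycles, refers to the reduction tables and also gives no step size.

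**Counts that delay a cycle.** Section 9.2.1 says "On day 1 of each new cycle, patients must meet the following criteria" and lists ANC of at least 1.0 and platelets of at least 50 × 10⁹/L. Section 9.2.2 then says "The next cycle of treatment will not be initiated until the above conditions (section 9.3.1) are met" and "If ANC and platelet counts do not satisfy the requirements above after 2 weeks of withholding treatment, the subject will go off therapy". Section 13.0 gives this as a reason to stop: "Hematologic toxicity has not completely resolved or resolved to < grade 1 or baseline after 2 weeks of withholding treatment".

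**Dexamethasone, Cohort 1 cycle 1.** Sections 1.0, 4.2 and 9.0 list 20 mg on days 1, 2, 3, 8, 9, 15, 16 and 22. Footnote p in Section 10.0 lists days 1, 2, 8, 9, 15, 16 and 22. The same footnote gives carfilzomib on days 2 and 3.

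**The concern.** These are operative rules in the current text. The first two bear on who stays on therapy and at what carfilzomib dose; the third sets a dose. If two sections give different answers for the same patient, two investigators can each follow the protocol and act differently, and either action departs from one section.

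The numbering adds to the difficulty. Section 9.2.2 cites 9.3.1 for its restart conditions, but 9.3.1 is the non-hematologic rule, which asks for recovery to Grade 1 or baseline. A reader who follows that pointer reaches a standard that resembles Section 13 and not the counts in 9.2.1.

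**Working it through.** Most of this is a comparison of texts. The arithmetic is limited to dose levels and dose counts.

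**1. Carfilzomib cap against the tables** (Sections 13.0, 9.1.2, 9.3.3, 9.2.2 and 9.2.3)

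- Cohort 1: 36 → 27 → 20. Two one-level steps use the whole table, so the cap of 2 fits it.
- Cohort 2: 56 → 45 → 36 → 27 → 20. Two one-level steps end at 36, and 36/56 = 64% of the starting dose. The two rows below are 27/56 = 48% and 20/56 = 36%.
- With one-level steps, the 27 and 20 rows would need a third and a fourth reduction, which Section 13 does not allow.
- The one-level wording is in 9.3.3, which covers non-hematologic toxicity. The 9.2.3 note and the second bullet of 9.2.2 do not limit the step, so a larger step for low counts could reach 27 or 20 within two reductions.

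**2. Two-week day 1 delay** (Sections 9.2.1, 9.2.2 and 13.0)

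| Patient's course | Section 9.2.2 | Section 13 |
|---|---|---|
| Meets 9.2.1 before 2 weeks | Cycle starts | Not triggered; withholding has ended |
| Still below 9.2.1 at 2 weeks, usual baseline | Off therapy | Off therapy |
| First meets 9.2.1 at the 2-week check, not resolved, not below grade 1, not at baseline | Cycle starts | Off therapy |
| Below 9.2.1 at 2 weeks, but back at a low, disease-related baseline | Off therapy | May stay |

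Example for the third row: ANC is 1.0 at the 2-week check, platelets are adequate, and baseline ANC was 3.0 (an illustrative value). Section 9.2.1 is met. The neutropenia table in 9.2.3 pairs ANC below 1.0 with Grade 3 and below 0.5 with Grade 4, so 1.0 lies just above the protocol's Grade 3 limit. If the next band is Grade 2 (an assumption, because the protocol prints no cut-points), 1.0 is not below grade 1. It would fail even if the Section 13 sign was meant to include grade 1. It is not at baseline either.

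The fourth row can arise because Section 6.1 waives the entry counts when cytopenia is judged to be due to disease. An illustrative case is a baseline ANC of 0.8.

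**3. Pointers**

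- Section 9.2.2 cites 9.3.1 twice where the day 1 criteria are in 9.2.1.
- Sections 9.2.2 and 9.3.3 each cite 9.2 for dose-reduction tables that are in 9.1.
- That makes four pointers to correct.

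**4. Dexamethasone, Cohort 1**

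- Section 9.0: cycle 1 = 8 × 20 = 160 mg; cycle 2 = 7 × 20 = 140; cycles 3–4 = 2 × 6 × 20 = 240; cycles 5–8 = 4 × 6 × 10 = 240. Total 780 mg.
- Footnote p: cycle 1 = 7 × 20 = 140 mg. Total 760 mg.
- Difference: 20 mg, which is 20/160 = 12.5% of cycle 1 and 20/780 = 2.6% over 8 cycles.
- The Section 10 calendar has no day 3 column, so it does not settle the point.

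**The case against.** **On the cap.** An investigator can reduce down the table and stop when a third reduction is needed, so both texts can be obeyed together. This stands. A reader might infer that the two sections contradict each other, or that the lower rows can never be reached. The documents support neither reading, because a larger step for low counts is left open.

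**On the counts.** Once the day 1 criteria are met the cycle starts and withholding ends, so the Section 13 bullet rarely comes into play. This also stands. A reader might infer that Section 13 is stricter for every delayed patient. The divergence is confined to a first pass at the 2-week check and, in the other direction, to patients with very low baseline counts. The example also needs one assumption about grades that the protocol does not print. The narrowness limits the size of the problem, but opposite instructions remain for the patients it reaches.

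**On the pointers.** The phrase about the above conditions in 9.2.2 already tells the reader that 9.2.1 is meant. That is fair, and the wrong number is probably a slip. It still names a different rule.

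**On dexamethasone.** Three sections agree on day 3, and the Cohort 1 list in footnote p is abbreviated in other ways: it also leaves out acetaminophen and diphenhydramine. The intent is therefore clear and the slip is small, but the footnote is part of the dosing schedule.

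**Conclusion.** All three mismatches are in operative text. They differ in weight.

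- **Day 1 delay:** a genuine conflict for a narrow group. The documents give no basis for a patient count. It rests on reading Section 13's 2-week bullet as covering day 1 delays and on taking Grade 2 as the band just above the Grade 3 limit for ANC.
- **Dexamethasone:** a plain omission of one 20 mg dose.
- **Carfilzomib cap:** minor. It affects only Cohort 2 patients who need a third reduction. With one-level steps their lowest dose is 36 mg/m² against a tabulated 20. The documents do not show whether the cap or the table reflects the intent.

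A reader might infer that these rules damage the primary analysis, because Section 13 also makes patients removed off-study in cycles 1–4 not evaluable and replaceable. The documents do not support going that far. The rules examined here take patients off therapy, and Section 13 lists off-study criteria separately. Section 14 counts a best response of MRD negativity within 8 cycles, so stopping therapy does not by itself cancel a negative result already reached. No number of affected patients can be derived. No effect on the Simon design is shown, and its operating characteristics were not part of this check.

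**What to change.** 1. **Carfilzomib cap.** The sponsor should state either that the cap is cohort-specific (2 in Cohort 1, 4 in Cohort 2) or that the 27 and 20 mg/m² rows are removed from the 56 mg/m² table. Raising the cap loosens a toxicity stopping rule. Deleting the rows raises the lowest Cohort 2 dose from 20 to 36 mg/m². Either is a clinical dosing decision and more than a change of wording.

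2. **Section 13 hematologic bullet.** Split it into three parts:
   - Day 1 delay from ANC or platelets: off therapy if the 9.2.1 criteria are not met after 2 weeks.
   - Hold during a cycle for ANC or platelets: use the 9.2.3 resume counts (ANC at least 1.0, platelets at least 25 × 10⁹/L), and off therapy if they are not met after 2 weeks. The limit must be kept, because 9.2.3 has none. Without it, a hold from day 8 could run 21 days to the next day 1 and then 14 more, 35 days in all.
   - Other hematologic toxicity: keep the present wording.

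   The text is short, but the Section 9 standards are usually looser than Section 13, so the sponsor should confirm the change on clinical grounds.

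3. **Pointers.** Change both citations of 9.3.1 in 9.2.2 to 9.2.1. Change the dose-table citations in 9.2.2 and 9.3.3 from 9.2 to 9.1. Wording only.

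4. **Footnote p.** Add day 3 to the Cohort 1 cycle 1 dexamethasone days. Wording only.

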14.0 BIOSTATISTICS

Primary Objective:

This is a phase II study to assess the efficacy of up to 8 cycles of combinational therapy with daratumumab, carfilzomib, lenalidomide, and dexamethasone in newly diagnosed multiple myeloma (MM) patients. The primary objective of the study is to assess the rate of MRD negativity at the end of planned treatment up to 8 cycles for the combination therapy using multiparametric flow cytometry. Patients with < PR after completing 4 cycles will be included in the analysis of the primary objective and will be considered MRD positive. Patients who receive any study drug and have at least one post-baseline disease assessment will be considered evaluable for the primary endpoint. The rate of MRD negativity will be assessed for each cohort, separately.

This study is designed to distinguish between an unpromising MRD rate of 40% and a promising rate of 60%¹. The unpromising rate of 40% is based on the 1st generation sequencing-based MRD rate in the referenced Korde et al study. The flow cytometry-based MRD assessment that will be used as part of this study has been shown to have similar performance as the sequencing-based MRD assessment used in that study.

The study includes two cohorts, which of each will receive up to 8 cycles of combination therapy. The two cohorts are defined based on the schedule and dosing of carfilzomib. These cohorts are described in Section 4.0. The following Simon two-stage design will be evaluated separately for the two cohorts.

Using a Simon's minimax two-stage design, the first stage of the study will enroll 28 patients. If at least 12 have a best response of MRD negativity within 8 cycles of therapy, the study will continue to enroll remaining patients up to a total of 41 patients. If, after 28 patients have accrued, it is uncertain whether the response threshold will be met, accrual will be held until the determination can be made. If 21 of the 41 patients have a best response of MRD negativity within 8 cycles of therapy the study will be considered to be successful. The study is designed to have a type I error and a type II error of 0.10. The maximum sample size is 41 patients.

The study includes safety suspension rules; throughout the study we will monitor for grade 3 or higher heart failure. These safety suspension rules will be applied separately in the two cohorts. In the event that the rule is crossed (see Table below), the study will be suspended for that cohort and all safety data will be reviewed by the PI. We will report all SAEs per standard guidelines (Section 17.2). In addition, throughout the study we will monitor for grade 4 or higher adverse events related to study drugs; if the PI notices there is a safety signal, the study will be suspended and all safety data will be reviewed by the PI.

Failure Type	# of failures needed to suspend the study	Failure rate in the population	Probability boundary is crossed
Heart failure/Ischemic heart disease (grade 3 or higher) Or grade 4 or higher adverse events due to study drug.	3 in the first 17 patients 4 in the first 29 patients 5 patients at any point	0.05	0.1
		0.2	0.95

The above numbers apply for each of the cohorts. Each cohort will be assessed independently.

Secondary Objective. Objectives 1, 2, and 3 below will be evaluated separately for the two cohorts.

1. To evaluate the safety and tolerability of the combination therapy. Toxicities will be summarized by grade and cycle of therapy. Patients who receive any study drug will be included in this assessment.
2. To evaluate the rates of best overall response (partial response (PR) or better), very good partial response (VGPR) or better, and complete response (CR) or stringent CR (sCR) for the evaluable patients. See section 12.0 for response definitions. Response proportions along with exact 95% confidence intervals will be reported.
3. Kaplan-Meier methods will be used to estimate overall and progression-free survival. . Patients who receive any study drug will be included in this assessment.
4. To compare MRD techniques of multi-parametric flow cytometry with 1) next-generation sequencing and 2) mass spectrometry using summary statistics. Rates of concordance for the measures will be estimated. This will be evaluated among all MRD assessments.
5. To create a bone marrow, urine, stool, and peripheral blood sample bank. These samples may be used to later evaluate biological activity of daratumumab, carfilzomib, lenalidomide, and dexamethasone. Potential analyses include sequencing and gene expression profiling on pre and post therapy bone marrow samples, identification of potential biomarkers (blood, urine, stool, bone marrow aspirates) associated with clinical outcomes.

Exploratory Studies:

1. The gene panel myTYPE (or alternative equivalent platform) will explore whether any mutations appear to be associated with response to therapy or toxicity associated with therapy. This analysis is for hypothesis-generation, and all results will be cautiously interpreted. Fisher's exact test may be used to assess any potential association. The variant allele frequency (VAF) will be summarized for each mutation.
2. myTYPE (or alternative equivalent platform) will also be evaluated using samples at the time of progression of disease or during an ongoing response and will be compared to the pre-treatment baseline samples to explore whether pathways leading to emergence of resistance to the drug regimen can be identified. Similar to the previous objective, this aim is for hypothesis generation, and all results will be cautiously interpreted. Changes in the VAF from baseline will be summarized for patients with an ongoing response and for patients who have progression of disease. A paired t-test may be used to further describe this association.
3. To evaluate the effects on stem cell mobilization quality in patients receiving daratumumab, carfilzomib, lenalidomide, and dexamethasone. Examples of data being collected but not limited to will include the following: number of patients undergoing stem cell mobilization, demographics, cycles received prior to stem cell mobilization, CD34 blood

counts prior to collection, total stem cell yield, mobilization failure rates, and subsequent attempts of mobilization.

The proposed study will enroll 41 newly diagnosed multiple myeloma patients seen at MSKCC into each of the two cohorts. Currently, we see over 250 new patients per year and we anticipate enrolling 2-4 patients per month on this study. Thus, we expect to have the study fully enrolled 12-24 months after opening of the study.

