In the past decade, multiple myeloma patients have reached deeper response rates with use of effective anti-myeloma therapeutics, immunomodulatory agents and proteasome inhibitors, approximating up to 75% patients achieving near-complete response (>90% decrease in monoclonal protein) or complete response (100% decrease in monoclonal protein). In general, improved therapeutics and deeper response rates have resulted in improved overall survival of multiple myeloma patients across most age groups. As a result, there has been an increasing demand for the development of sensitive assays to detect minimal residual disease (MRD) in treated MM patients. In MM patients receiving autologous stem cell transplant, MRD-negative status using multi-parametric flow cytometry (MFC) is associated with improved progression free survival and overall survival. Similar studies using next generation sequencing methods for MRD have also been shown to be associated with improved outcomes in MM MRD-negative patients. In our prior study, among the 25 patients with CR/sCR that were assessed by MFC for immunophenotypic abnormal plasma cells; 25 out of 25 were negative for (MRD with an overall MRD negative rate of 25/43 (58)% (*2 patients did not have evaluable samples) using MFC. Using next generation sequencing molecular tests, the CR/sCR MRD negative rate was 13/33 (39%) (*12 patients did not have evaluable samples) (Sequentia platform). In patients with NDMM treated with CRd, 12-month progression-free survival for MRD-negative vs MRD-positive status by flow cytometry and next-generation sequencing was 100% vs 79% (95% CI, 47%-94%; $P < .001$) and 100% vs 95% (95% CI, 75%-99%; $P = .02$), respectively.

Minimal Residual Disease Platforms

A recent survey including 30 major institutions in the US found major heterogeneity in MRD testing of multiple myeloma by flow cytometry²². In brief, there was considerable variation in the number of bone marrow cells analyzed (events) and number of abnormal plasma cells needed to define the presence of MRD, which affects maximum possible sensitivity. The maximum detection sensitivity ranged from 0.0005% to 0.02%, a 100-fold difference in sensitivity. Also, the variation in antibodies studied and definition of an abnormal plasma cell by flow cytometry affected the ability to differentiate normal from neoplastic plasma cells.

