In 2015, the Department of Laboratory Medicine developed, validated and implemented in the 10-color platform in collaboration with the Myeloma Service and the International Myeloma Foundation. The MSK single tube 10-color flow cytometry platform demonstrates similar results to Euroflow and is already in use under clinical practice. Because there is currently no data available to compare the sensitivity of the MSK model and molecular MRD assays, as a secondary endpoint, we will compare our 10-color flow cytometry platform against next generation sequencing and mass spectrometry. These studies will help us to better understand and further develop details of various MRD methods.

Daratumumab in Combination with Carfilzomib, Dexamethasone and Lenalidomide

The results of the interim analysis show 11 participants have reached MRD negativity with an average of 5.36 cycles in Cohort 1 while 10 participants have reached MRD negativity with an average of 4.5 cycles in Cohort 2. There are 2 participants and 18 participants pending a best MRD response within 8 cycles of combination therapy for Cohort 1 and 2, respectively. As of May 2019, Cohort 2 has shown a 100% MRD negativity rate as a best response within 8 cycles of combination therapy. Cohort 2 is based on weekly dosing schedule that reduces the number of visits by 50% from Cohort 1 with Carfilzomib 56 mg/m² per dose.

Randomization Cohort Treatment Arms

Randomization allows objectivity for assigning treatment arms. Attal et al. published results that showed participants treated with RVD induction therapy achieved MRD negativity at 65%. However, overall survival at 4 years between the transplantation group and the RVD only alone group was similar (81% and 82%, respectively)⁴⁷. In a later study, Perrot et al. showed 25% MRD negativity was achieved at least once during maintenance with in 127 patients who were treated with RVD induction therapy alone⁴⁸.

Evidence supports KRd induction is favorable induction therapy for NDMM and SMM as one study has shown 28 patients with NDMM and the 12 with SMM achieved a-near CR with 28 of 28 found to be MRD negative from the JAMA Oncology paper on the NCI KRd phase 2 study (Korde et al, 2015)⁴⁹.

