For patients undergoing MRD or end of study assessment, the first pulled bone marrow sample will be sent for multi-parametric flow cytometry as a priority. This will be a centralized Next-Gen Sequencing (NGS) based MRD testing. Flow cytometry based assay to rule out MRD (defined as less than 20 abnormal plasma cells) in bone marrow aspirates of CR/sCR/VGPR patients. CR/VGPR and MRD 10^{-5} negative in the bone marrow is confirmed by using a validated method with a sensibility of at least 1 in 10^{-5} nucleated cells. Patients with $< \text{CR/sCR/VGPR}$ are considered MRD positive. We will use the MSKCC flow cytometry MRD method which is based 10-colors in a single tube. This test has sensitivity to identify 1 myeloma cell in 100,000 bone marrow cells, or better. The test demonstrates highly similar results when compared to the current Euroflow approach. This test is validated and already in clinical use at MSK. Immunophenotyping of aberrant plasma cells by flow cytometry currently involves, but is not limited to, the use of the following reagents: CD138, CD19, CD45, CD38, and CD56. Characteristic changes in immunophenotypically abnormal plasma cells (CD38 bright and/or CD138 positive) include but are not limited to decreased or absent CD19 and CD45, decreased CD38, increased CD56, decreased CD27, decreased CD81, increased CD117. For patients with non-evaluable samples at MRD assessment, patients can opt for repeat MRD assessment or continue to receive a total of 8 cycles of DKRd. A patient with CR/sCR/VGPR who has undeterminable MRD status will be treated as MRD+ for the primary endpoint.

Traditional Response Criteria from International Myeloma Working Group Criteria for Multiple Myeloma⁶⁵ (KUMAR ET AL, LANCET ONCOL 2016):

Evaluation of Response Criteria

- a) Stringent Complete Response (sCR)
 - Complete Response as defined below plus: Normal FLC ratio and absence of clonal cells in bone marrow by immunohistochemistry or immunofluorescence (presence/absence of clonal cells is based on the kappa/ lambda ratio).
- b) Complete Response (CR)
 - Negative immunofixation on the serum and urine and disappearance of any soft tissue plasmacytomas and $\leq 5\%$ plasma cells in bone marrow
- c) Very Good Partial Response (VGPR)

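### The 40% null is a CR/sCR-only MRD-negative rate, but the trial also scores MRD-negative VGPR, so the 0.10 type I error does not cover a regimen that is merely no better than KRd

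*Combined protocol and SAP*

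**What the plan says.** **Design.** Section 14.0 sets the two rates: "This study is designed to distinguish between an unpromising MRD rate of 40% and a promising rate of 60" per cent. It says that the 40% comes from the sequencing-based MRD rate of the earlier KRd study, and it asserts that the flow assay used here performs similarly to that sequencing assay. Each cohort follows a Simon minimax design: "the first stage of the study will enroll 28 patients", and accrual continues on this condition: "If at least 12 have a best response of MRD negativity within 8 cycles of therapy". Success is 21 of 41. "The study is designed to have a type I error and a type II error of 0.10".

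**Benchmark.** Section 3.0 (Minimal Residual Disease Testing in Myeloma) describes the KRd figure as follows: "Using next generation sequencing molecular tests, the CR/sCR MRD negative rate was 13/33 (39" per cent), with 12 patients lacking evaluable samples. By flow, the same study had 25 negatives among 43 patients, and those 25 are the 25 patients in CR/sCR.

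**Endpoint.** Section 12.0 (Minimal Residual Disease) sets a wider numerator: "Flow cytometry based assay to rule out MRD (defined as less than 20 abnormal plasma cells) in bone marrow aspirates of CR/sCR/VGPR patients". Only patients below VGPR are automatically MRD positive, and the MRD response criteria in the same section again name VGPR/CR. On missing results it says: "A patient with CR/sCR/VGPR who has undeterminable MRD status will be treated as MRD+ for the primary endpoint".

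**A second count from the same study.** Section 3.0 (Randomization Cohort Treatment Arms) reports that 28 newly diagnosed patients "achieved a-near CR with 28 of 28 found to be MRD negative".

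**The concern.** The null and the endpoint do not admit the same patients. In the KRd benchmark, a patient had to be in CR/sCR to count as MRD negative. In this trial an MRD-negative patient in VGPR counts as well. Section 14.0 neither mentions nor adjusts for the difference.

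The widening can only raise the rate that a regimen equal to KRd would show on this endpoint. If any KRd patient in VGPR would have been MRD negative, part of the gap between 40% and the observed rate reflects the definition and not the added drug. At stake is the like-for-like reading of a positive result: 21 of 41 on the wide endpoint would be taken as improvement over KRd with a 10% false-positive risk, when the risk for that particular claim may be higher. This holds in each cohort separately, and it is distinct from whether flow and sequencing agree.

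**Working it through.** **Inputs.** From Section 14.0: p0 = 0.40, p1 = 0.60, at least 12 of 28, then at least 21 of 41, error rates 0.10 and 0.10. From Section 3.0: 13/33 by sequencing (45 − 12 = 33), 25/43 by flow, 28 near-CR patients all MRD negative.

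The 33 is everyone with an evaluable sample, not only the 25 CR/sCR patients. So only the numerator is restricted to CR/sCR.

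**Formula.** For a true rate p on the trial's endpoint:

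P(success) = sum over x = 12 to 28 of Bin(x; 28, p) × P(Bin(13, p) ≥ 21 − x).

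**Step 1: reproduce the design.** p = 0.40 gives 0.0951 and p = 0.60 gives 0.9009. A full search for the minimax design with both errors at most 0.10 returns the same 12/28 and 21/41. The stated design is correct at its own null.

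**Step 2: a regimen no better than KRd on the wider endpoint.** Neither the VGPR share of the KRd study nor MRD negativity within VGPR is in the documents. The VGPR-inclusive KRd rate is therefore an assumption, shown over a range.

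| Assumed VGPR-inclusive KRd rate | P(success) |
|---|---|
| 40% (no MRD-negative VGPR) | 0.095 |
| 42% | 0.148 |
| 45% | 0.256 |
| 47% | 0.346 |
| 50% | 0.496 |

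In whole patients added to 13/33:

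| Extra MRD-negative VGPR patients | Rate | P(success) |
|---|---|---|
| 0 | 13/33 = 39.4% | 0.082 |
| 1 | 14/33 = 42.4% | 0.161 |
| 2 | 15/33 = 45.5% | 0.276 |
| 3 | 16/33 = 48.5% | 0.419 |

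**Step 3: what the 28 against 25 suggests.** The near-CR count exceeds the CR/sCR count by 28 − 25 = 3. Section 3.0 glosses near-CR as a fall of more than 90% in monoclonal protein, and the VGPR criterion in Section 12.0 includes a reduction of 90% or more, so near-CR plausibly lies within VGPR or better. Carrying the three patients onto the 40% null:

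- in proportion, 0.40 × 28/25 = 44.8%: P(success) = 0.248;
- additively, 0.40 + 3/45 = 46.7%: 0.330;
- additively, 0.40 + 3/43 = 47.0%: 0.345.

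This assumes that the three are a depth effect and would also be sequencing-negative. If each were sequencing-negative only with probability 13/25 (an assumption, from 13 sequencing against 25 flow negatives), the rate is 0.40 + (3/45)(13/25) = 43.5% and P(success) = 0.20.

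**Step 4: the offset.** This trial counts undeterminable MRD as positive, whereas the benchmark dropped 12 of 45. With this trial's rule applied to the sequencing count, the rate is 13/45 = 28.9%. Three extra negatives make 16/45 = 35.6%, with P(success) = 0.028. Five are needed to reach 18/45 = 40%.

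**The case against.** The strongest reply has four parts.

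- **Type I error is defined at the stated null, and there it is 0.095.** This stands. A reader might infer that the trial's type I error is really about 0.25 to 0.34. The documents do not support that: those are pass probabilities at an assumed rate of roughly 45–47%. Nor is it right that 21 of 41 fails to reject 40%; it does reject it, for the endpoint as defined. What does not follow is improvement over KRd on a like-for-like count.
- **The three extra patients may not be VGPR patients.** Section 3.0 does not name the assay behind 28 of 28, while the 25 are flow negatives. The 25 and the 28 are cited to different reports, from 2013 and 2015. Time to sCR ranged up to 18 cycles, so longer follow-up could explain the difference. This stands, and it is why 45–47% is a suggestion and not an estimate.
- **The handling of undeterminable MRD works the other way.** This stands for direction: on the sequencing benchmark the net bias is not established. Its size in this trial is probably smaller than 16/45 implies, because by flow only 2 of 45 KRd patients lacked evaluable samples and Section 12.0 allows repeat assessment.
- **VGPR patients may seldom be tested.** Section 1.0 triggers on-treatment MRD testing at CR/sCR. But Section 9.4.4 also calls for the MRD marrow at end of therapy, so VGPR patients can still score.

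None of this removes the mismatch. It prevents attaching a single number to it.

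**Conclusion.** The mismatch is real and stands in the documents: the null has a CR/sCR-only numerator, the endpoint admits VGPR, and Section 14.0 does not reconcile them. The design is valid as a test of a 40% rate on the trial's own endpoint (0.095). It does not limit to 0.10 the chance of success for a regimen merely equal to KRd.

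That chance exceeds 0.10 if the VGPR-inclusive KRd rate is above 40%: 0.15 at 42%, 0.26 at 45%, 0.35 at 47%, 0.50 at 50%. The 28-against-25 comparison points to about 45–47%, on two unverified assumptions: that the three extra patients reflect response depth, and that sequencing would also have called them negative. The rule on undeterminable MRD pulls the other way by an unknown amount. Assay equivalence is taken here as Section 14.0 asserts it.

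This is a should-fix: a matter of wording, sensitivity and reporting, not an invalid design.

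**What to change.** In Section 14.0:

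1. State that the 40% benchmark counts MRD negativity in CR/sCR only. State that the 0.10 type I error refers to a true rate of 40% on this trial's endpoint (CR, sCR or VGPR, undeterminable counted as positive), not to being no better than KRd.
2. Give the pass probability over the range in the tables, with the assumptions and the opposing effect of undeterminable samples.
3. Report MRD negatives per cohort split into CR/sCR and VGPR.
4. Claim improvement over the KRd 40% figure only if at least 21 of 41 are MRD negative in CR/sCR. If the true CR/sCR MRD-negative rate is 40%, P(Bin(41, 0.40) ≥ 21) = 0.0965, so the chance of a false claim on that count stays below 0.10 whatever the first stage does.
5. Keep 12/28 and 21/41 as the design rule.

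Raising the threshold is not recommended. Testing 46.7% against 66.7% with 24 of 41, for example, gives a type I error of 0.086 but power of 89.6%, a type II error of 0.104 against the stated 0.10. It would also fix an assumed null and move the threshold after the interim MRD results in Section 3.0 are known.

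The cost is some wording and one extra tabulation of data already collected, with no added patients or marrows. The downside is that the stated operating characteristics look less favourable and a claim of improvement over KRd becomes harder to make.
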